## 5. Study enrollment and withdrawal

### Patients

- Of any gender
- Over 18 years of age
- Have a previous diagnosis of ulcerative colitis
- Have had IPAA surgery, and
- Have been diagnosed with pouchitis
- Be able to understand and complete study procedures as determined by the investigator
- Be able to speak either Danish or English
- Be able to comply with study procedures for the length of the study
- Use a highly effective contraception method for the duration of the trial as mentioned below (until day 30 in Phase I and until day 37 in Phase II). In men, there is no evidence of GM-CSF or

the administered antibiotics increasing risk for genetic damage in the spermatozoa that can result in embryopathies.

Written informed consent must be obtained.

#### Exclusion criteria

- Patients with a previous allergic reaction to GM-CSF, metronidazole or fosfomycin
- Patients who are currently under antibiotic treatment or have received antibiotic treatment within the past 30 days
- Patients currently pregnant or breastfeeding. A pregnancy test (serum Hcg) must be negative before inclusion into the trial.
- Patients with ASA IV classification (American Society of Anesthesiologists physical status classification)
- Patients with severe pulmonary disease
- Patients with autoimmune thrombocytopenia
- Patients with severe renal impairment (eGFR < 40 ml/min)
- Patients with alcohol use disorder or history of drug abuse
- Patients currently in treatment for any malignant or hematological disease
- Patients with a previous history of cancer will be excluded from the study (except for patients with well-treated and stabile cancer after a control period of more than two years).
- Patients with anticipated compliance problems as determined by the investigator

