## 1. Summary

A definitive cure for patients with treatment-refractory ulcerative colitis is proctocolectomy with IPAA (restorative ileal pouch anal anastomosis) (1). Up to 50% of all patients develop “pouchitis” within the first five years after surgery, an inflammatory condition that is as yet poorly understood and without official consensus on treatment (2). Treatment modalities include oral antibiotics as well as immunomodulators, steroids, probiotics and biological agents, but up to 20% of these patients develop chronic, treatment-resistant pouchitis, which can result in pouch failure and the need for reoperation with the possible creation of an ileostomy (11,12).

The etiology of pouchitis is thought to be similar to other inflammatory bowel diseases, in that genetic and bacterial factors, a compromised gastrointestinal barrier and immunological components seem to play a role. Its pathogenetic mechanisms seem to mimic Crohn’s disease, in which smaller studies have shown some effect of systemically administered GM-CSF (granulocyte-macrophage colony stimulating factor) on the gut macrophage function in clearing microorganisms and maintaining the mucosal barrier (3–6).

We hypothesize that GM-CSF will have an effect in the treatment of pouchitis because of its similarity to that of Crohn’s disease. In order to maximize effect on the inflamed mucosa and minimize systemic side effects, we intend to administer it locally in the pouch. In a safety and proof-of-concept intervention study we will combine 50 µg GM-CSF with two well-known antibiotics, 400 mg Fosfomycin and 100 mg metronidazole, to target both the suspected immunological as well as the bacterial role in the pathogenesis of pouchitis.

The effect on the pouch will be assessed endoscopically and histologically by taking biopsies that will also be examined for changes in the microbiome. Patients will be clinically examined and have blood samples taken to monitor for adverse reactions. The primary outcome measure will be an assessment of adverse reactions and tolerability of the drug. Secondary outcome measures will be a change in the pouchitis disease activity index (PDAI), a change in the microbial diversity, and a change in inflammatory markers.

This study is based on a non-randomized trial design with an open-label single group assignment.

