Other treatment modalities include probiotics, immunomodulators, steroids and biological agents (12,13). Up to 20% of patients with acute pouchitis can develop chronic pouchitis or chronic refractory pouchitis (14). While these can also be manageable with medical treatment, a small percentage of patients develop therapy-resistant pouchitis. A meta-analysis in 2017 by Segal et al. suggested that, on average, remission can be achieved in up to 59% of patients, but that chronic pouchitis still is challenging because the pathogenesis behind it is not fully understood (15). In therapy-resistant pouchitis, surgery with fecal diversion with the construction of an ileostomy is the treatment of choice and this results in the loss of anal defecation. Pouch failure ranges between 3.5% after 5.5 years to up to 9% after 10 years in various studies (16,17).

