### **Bias**

This study is an open-label proof-of-concept study with a single treatment arm. There is no blinding of patients or the investigator. The only blinded examination is the pathology examination of mucosal biopsies of the pouch and 16S rRNA sequencing. The pathologist is unaware of whether samples are taken before the application of the study drug or after. Therefore, the histology of the PDAI should not be influenced by bias.

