#### Reasons for withdrawal

A patient will be discontinued from participation in the study

- if any clinical AE or AR (adverse event or reaction), laboratory abnormality, intercurrent illness, or other medical condition or situation occurs which suggests that continued participation in the study would not be in the best interest of the patient. This also concerns the necessity of initiating a particular drug treatment, e.g. antibiotics for infection or taking a 'rescue drug' for a medical condition, that interacts with the study drug
- when developing any of the exclusion criteria

Patients can voluntarily withdraw from participation in this study at any time as well as withdraw from receiving the study intervention for any reason. The patients will be informed of this right in accordance with the Helsinki Declaration.

The investigator can withdraw a patient if the investigator considers that the safety of the patient is compromised by the participation in the study. In that case, the investigator must inform the patient about the reason for withdrawal.

When patients withdraw from the study, reasons for withdrawal, if given, will be documented in the CRFs (Case report forms). The number of dropouts and withdrawals will be reported. No further data will be collected from the patients withdrawing from the study; however, the previously collected data will be part of the final data analysis unless the patient specifically requests all data to be deleted. Patients that have received the study medicine will be contacted by telephone two weeks after receiving the study medicine, to ensure patient wellbeing. This data after withdrawal from the study, will not be collected and is meant solely to ensure the safety of the patient.

In case of withdrawal due to AE or AR, safety data will be collected and the patient will be followed until given appropriate care under medical supervision or until symptoms of any AE or AR resolve or become stable.

Participants who discontinue early will be replaced. This concerns all patients that have not undergone the second endoscopy. In case of withdrawal due to a serious adverse event (SAE) or serious adverse reaction (SAR), continuity of inclusion will be discussed with the sponsor.

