#### Study procedure - evaluation

##### Clinical evaluations

At the first baseline visit, a thorough medical history will be taken both by using a patient interview as well as by using past medical records from the electronic health records. A list of current medications is made, where all currently taken medications should be included, both prescription and over-the-counter medicine, as well as medicine taken within the last 30 days. The patients PDAI score must be recorded.

The physical examination will include a measurement of vital signs (blood pressure, pulse, temperature, respiratory frequency), as well as cardiopulmonary, gastrointestinal and gross neurological examination. Current weight, height, BMI (body mass index), ASA score, performance status.

Subsequent visits will include a short update of the medical history, an update of the PDAI as well recording any adverse reactions during the study period. A clinical symptom-directed examination is done if the investigator deems this necessary.

All data is recorded in Easytrial by direct entry, using autoquery to minimize faulty data entry.

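### Only antibiotics are restricted before entry, so the effect of another recently started pouchitis treatment could be credited to the study drug

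*Protocol*

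**What the plan says.** The Summary lists the treatments in use: "Treatment modalities include oral antibiotics as well as immunomodulators, steroids, probiotics and biological agents". Section 2 repeats the list: "Other treatment modalities include probiotics, immunomodulators, steroids and biological agents".

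The eligibility criteria act on one of these classes only. The exclusion list, in the Summary and again in section 5, removes "Patients who are currently under antibiotic treatment or have received antibiotic treatment within the past 30 days". The disease criterion for inclusion is "Have been diagnosed with pouchitis", with no condition on background therapy.

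Other medicines are recorded. Section 7 (Clinical evaluations) asks for all current medicines "as well as medicine taken within the last 30 days". Appendix 2 schedules a medication review at screening, Day 1, the second endoscopy and the final call. Appendix 3 has fields for past probiotics and diets. No rule is attached to what is recorded.

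Section 5 (Reasons for withdrawal) discontinues patients when continuing would not be in their interest. As an example it gives the need to start a drug: "antibiotics for infection or taking a 'rescue drug' for a medical condition, that interacts with the study drug". A second bullet discontinues anyone who comes to meet an exclusion criterion.

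On design, section 3 (Bias) states: "This study is an open-label proof-of-concept study with a single treatment arm".

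**The concern.** With no comparator, each patient's baseline is the only reference. The before/after difference can be read as a study-drug effect only if nothing else that acts on the PDAI changed around Day 1. The protocol applies this reasoning to antibiotics but not to the other classes it calls pouchitis treatments.

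A steroid, biologic, immunomodulator or probiotic started or increased just before Day 1 could still be taking effect between the two endoscopies. That would push the PDAI, and possibly CRP, towards apparent benefit, and it could also alter the microbiome comparison. A recent reduction could push the other way. The Phase II primary outcome rests on 12 patients, so a single case is visible in the result. Section 8 also intends the data to inform future sample-size calculations.

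**Working it through.** **1. Does any provision reach a non-antibiotic pouchitis treatment begun before Day 1?**

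- Eligibility (Summary and section 5): no. Only antibiotics are named.
- Withdrawal, new-drug clause (section 5): no. It concerns drugs that become necessary during participation.
- Withdrawal, exclusion-criterion clause (section 5): no. It catches an antibiotic started later, but the other classes are not exclusion criteria.
- Medication review (section 7, Appendices 2 and 3): it records the drug and triggers nothing.
- Completed test person (section 5): defined by procedures received, without regard to co-treatment.
- Analysis set (section 8): every completed test person is analysed.
- Section 3, Bias: discusses blinding only.

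Such a patient therefore enters, completes and is analysed like any other.

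**2. The denominator.** Section 8 states that 9 patients are needed at the 1% level and adds 3, giving 9 + 3 = 12. It gives no effect size, standard deviation (SD) or power. All that can be checked is the smallest two-sided p that a paired sign or signed-rank test can reach, 2 × 0.5^n. This is 0.0078 at n = 8 and 0.0039 at n = 9, so 9 is compatible with such an argument. The present point uses only the 12.

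**3. Responder proportion.** Section 3 counts a PDAI fall of 3 points or more as improvement. Suppose k of 12 patients reach it because of the other therapy and would not have done so otherwise. The proportion then rises by k/12:

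- k = 1: 1/12 = 8.3 percentage points
- k = 2: 2/12 = 16.7 percentage points
- k = 3: 3/12 = 25.0 percentage points

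The values of k are assumptions; the protocol gives no frequency.

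**4. Paired comparison, as an illustration.** Assumptions not in the protocol: the study drug has no effect, the co-treatment lowers PDAI by 3 points, changes are normally distributed with an SD of 2 or 3, and an exact two-sided Wilcoxon signed-rank test is used at 0.05. The mean change credited to the study drug is −3k/12. The last column is the simulated chance of a significant apparent improvement (40,000 replicates per setting).

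| k of 12 | Mean change | SD 3 to SD 2 |
|---|---|---|
| 0 | 0 | 0.021 |
| 1 | −0.25 | 0.033 to 0.038 |
| 2 | −0.50 | 0.051 to 0.065 |
| 3 | −0.75 | 0.076 to 0.102 |
| 4 | −1.00 | 0.115 to 0.169 |

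The inflation is modest at one or two patients and clear at three or four. Ties from whole-number PDAI scores were not modelled.

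**The case against.** The strongest reply concerns likelihood. Section 7 (Screening) recruits patients with a flare of acute pouchitis, which section 2 defines as lasting under four weeks. The local standard for them is ten days of an oral antibiotic. That class is washed out before entry and given only after the second endoscopy, so the treatment a flare would normally trigger is already controlled. This stands, and it makes the problem probably infrequent. It does not remove it: the formal criterion admits any diagnosed pouchitis, including the chronic form that section 2 describes as persisting despite therapy.

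A reader might infer that a stable background is the trial's only protection against false attribution. The documents do not support that. Stable co-treatment would not deal with natural course, regression to the mean or expectation, and the protocol has another safeguard in pathology blinded to time point. The medication records would also let affected patients be identified afterwards.

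A reader might also infer that changes after Day 1 are wholly unregulated. They are partly covered. A later antibiotic leads to discontinuation. The phrase about interaction with the study drug may qualify only the rescue drug, so the new-drug clause can be read more broadly than pharmacological interaction. The firmer gap is before Day 1.

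Finally, section 10 concedes that the results cannot settle efficacy. That limits the consequence, but an avoidable bias still weakens a study meant to guide the next one.

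**Conclusion.** The point holds as an incomplete eligibility rule. Followed exactly, the protocol admits a patient who has just started or changed a treatment it calls active in pouchitis, and it credits any resulting PDAI fall to the study drug. Each such patient adds 8.3 percentage points to the Phase II responder proportion, provided the improvement comes from the other therapy and would not otherwise have reached 3 points.

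The number of such patients is unknown and probably low. The documents do not support a claim that flare patients commonly change these therapies, or that the Phase II result would be invalid. This is an inexpensive improvement worth making before enrolment.

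**What to change.** 1. In the eligibility criteria of the Summary and section 5, add an entry condition that probiotics, immunomodulators, steroids and biological agents have been unchanged for a stated period before Day 1. The clinical team should set the length. The 30 days already recorded under Clinical evaluations is a practical option, though the documents give no specific basis for it in these classes.
2. Word it as a condition at entry only; the inclusion list is the safer place. Written as an exclusion criterion, it would activate the withdrawal bullet on developing exclusion criteria, and patients who changed therapy later would be discontinued and replaced.
3. For changes between Day 1 and the second endoscopy, leave care unrestricted. Keep the patient in the analysis and count the patient as not improved in the responder outcome. That rule does not correct the other comparisons, so repeat the paired PDAI, CRP and microbiome analyses without such patients as a sensitivity analysis.
4. State how this fits with Reasons for withdrawal: a patient whom the investigator discontinues before the second endoscopy stays under the existing replacement rule, and the reason is reported.

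The cost is one eligibility line and a short analysis paragraph. The data are already collected and the sample size does not change. The downside is that a few recently changed patients are enrolled later or not at all, which matters somewhat at a single site and should be weighed when the look-back is chosen.

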#### A completed test person

A completed test person is defined as:

Phase I: a patient who received the therapeutic endoscopy, clinical examination and had pre-treatment blood samples drawn, and then came for a clinical appointment on day 7 with new blood samples drawn, clinical examination, and control endoscopy

Phase II: a patient who received the initial endoscopy, clinical examination and had pre-treatment blood samples drawn, and then received the enema daily for 7 days and came for a clinical appointment on day 14, when new blood samples were drawn, and clinical examination and control endoscopy performed

#### Reasons for withdrawal

A patient will be discontinued from participation in the study

- if any clinical AE or AR (adverse event or reaction), laboratory abnormality, intercurrent illness, or other medical condition or situation occurs which suggests that continued participation in the study would not be in the best interest of the patient. This also concerns the necessity of initiating a particular drug treatment, e.g. antibiotics for infection or taking a 'rescue drug' for a medical condition, that interacts with the study drug
- when developing any of the exclusion criteria

Patients can voluntarily withdraw from participation in this study at any time as well as withdraw from receiving the study intervention for any reason. The patients will be informed of this right in accordance with the Helsinki Declaration.

The investigator can withdraw a patient if the investigator considers that the safety of the patient is compromised by the participation in the study. In that case, the investigator must inform the patient about the reason for withdrawal.

When patients withdraw from the study, reasons for withdrawal, if given, will be documented in the CRFs (Case report forms). The number of dropouts and withdrawals will be reported. No further data will be collected from the patients withdrawing from the study; however, the previously collected data will be part of the final data analysis unless the patient specifically requests all data to be deleted. Patients that have received the study medicine will be contacted by telephone two weeks after receiving the study medicine, to ensure patient wellbeing. This data after withdrawal from the study, will not be collected and is meant solely to ensure the safety of the patient.

In case of withdrawal due to AE or AR, safety data will be collected and the patient will be followed until given appropriate care under medical supervision or until symptoms of any AE or AR resolve or become stable.

Participants who discontinue early will be replaced. This concerns all patients that have not undergone the second endoscopy. In case of withdrawal due to a serious adverse event (SAE) or serious adverse reaction (SAR), continuity of inclusion will be discussed with the sponsor.

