## Phase II – Proof of concept study

### Primary outcome measure

- Change in the pouchitis disease activity index (PDAI) – A decrease of 3 points or more will be determined as an improvement in PDAI from before application of the study drug to 7 days after application of the study drug

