## 8. Statistical considerations

We plan to include 6 patients in the Phase I study to test tolerability, and 12 patients in the Phase II study to test effectiveness of the treatment. The trial will end with the last visit of the last patient (Day 37 of the last patient). This is a safety and clinical proof-of concept intervention study, and we are, to the best of our knowledge, the first group to look into local treatment with GM-CSF and antibiotics of biofilm in patients with pouchitis after IPAA for ulcerative colitis. We expect this number of patients to be sufficient to provide the necessary experience in implementing the technique and form a basis for future studies, including future sample size calculation. This is based on calculations on number of patients required to achieve statistical significance of paired before-and-after comparisons by non-parametric tests. To achieve statistical significance at 1% level in Phase II, 9 patients are needed. As there is a risk of patients withdrawing from the trial prematurely or not receiving all interventions, we aim to include 3 additional patients.

Our primary objective is to test for adverse events or reactions in Phase I and a significant change in PDAI in Phase II, defined by a decrease of 3 points. Differences pre- and post-treatment will be described by means and standard deviations, or median and range when appropriate, and will be analyzed by the appropriate statistical tests. All patients described in chapter 5 as 'Completed test persons' will be included in the statistical analysis.

Microbial diversity changes will be analyzed using PERMANOVA (permutational analysis of variance). Other secondary objectives like change in WBC and CRP will be analyzed using the appropriate statistical tests.

Data will be analyzed using non-parametric or parametric statistics depending on the distribution of the data. P-values  $\leq 0.05$  are considered significant. Correction for multiple comparisons will be performed if needed. Descriptive statistics will be used for baseline characteristics.

Missing data will be handled depending on the type of data missing. If missing data results in a patient not being able to be defined as a 'Completed test person' (Chapter 5), the patient is excluded from the trial and a new patient will be recruited. If individual results are missing (e.g. laboratory values), the last known values will be used for analysis.

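### Minor: a Phase II completer who starts or increases a steroid, immunomodulator or biologic for pouchitis before the second PDAI can still be scored as improved

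*Protocol*

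**What the plan says.** The Phase II primary outcome in section 3 of the protocol reads: "A decrease of 3 points or more will be determined as an improvement in PDAI". It sets no condition on other treatment.

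Section 5 defines a Phase II completed test person as one who had the initial endoscopy, examination and blood samples, received the daily treatment for 7 days and "came for a clinical appointment on day 14, when new blood samples were drawn, and clinical examination and control endoscopy performed". Section 8 then states: "All patients described in chapter 5 as 'Completed test persons' will be included in the statistical analysis".

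On co-treatment, the section 5 exclusion criteria name one class of pouchitis drug: "Patients who are currently under antibiotic treatment or have received antibiotic treatment within the past 30 days". Section 2 recognises more: "Other treatment modalities include probiotics, immunomodulators, steroids and biological agents". The criteria neither exclude those classes nor ask for stable doses.

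The withdrawal rule in section 5 covers situations in which staying in the study is not in the patient's best interest. It extends to the need to start a particular drug, for example "antibiotics for infection or taking a 'rescue drug' for a medical condition, that interacts with the study drug". Developing an exclusion criterion is a second trigger. Patients who discontinue early are replaced, with the limit: "This concerns all patients that have not undergone the second endoscopy".

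In Phase II, Appendix 2 schedules the concomitant-medication review at screening, Day 1, Day 14 and Day 37. Adverse reactions are also assessed on Days 2-7, when the drug is given in hospital.

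**The concern.** The endpoint, the completer definition and the analysis set are all fixed in the protocol, and none of them looks at what else the patient took. A patient whose steroid is started or raised on Day 9, and whose PDAI then falls by 3 points at the second endoscopy, is counted as a success of the study drug.

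Phase II has one open arm, so no comparison group carries the same co-treatment and absorbs its effect. Section 8 also wants the data to support future sample size calculations, so an inflated improvement rate would carry forward into the next trial.

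**Working it through.** **1. Which rule applies to which drug.**

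- New antibiotic: meets an exclusion criterion, so the patient is withdrawn. This case is closed.
- New steroid, immunomodulator or biologic: not an exclusion criterion. Withdrawal depends on best interest and, in the rescue-drug example, on interaction with the study drug. Some such patients may be withdrawn, but nothing requires it.
- Higher dose of one of these drugs already taken at entry: the withdrawal text speaks of initiating a drug, so an increase is not clearly covered.
- Patient not withdrawn, all doses and visits done: a completer, analysed, and improved if PDAI falls by 3 or more.

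**2. When a change would be seen.** Daily hospital dosing and adverse-reaction assessment give contact on each of Days 2-7. The next scheduled contact is the Day 14 visit (window Days 13-16). An unnoticed change is therefore likely only from about Day 8. The Day 14 medication review falls at the same visit as the second endoscopy, and once that endoscopy is done the replacement rule no longer applies.

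**3. Direction.** Let X be the number improved as observed, and a the number of affected completers among them. Scoring the affected as not improved gives X − a, which cannot exceed X. Against that target, as-observed scoring leaves the rate unchanged or raises it.

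**4. Size for the improvement rate.** One affected patient:

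- 12 completers (the planned number): 1/12 = 8.3 percentage points
- 9 completers (the number section 8 says are needed): 1/9 = 11.1 percentage points

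**5. The protocol's own figure.** Section 8 bases the 9 patients at the 1% level on "calculations on number of patients required to achieve statistical significance of paired before-and-after comparisons by non-parametric tests". With no ties and every patient falling, the exact two-sided signed-rank p is 2/2^n:

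- n = 7: 2/128 = 0.0156
- n = 8: 2/256 = 0.0078
- n = 9: 2/512 = 0.0039

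The smallest n that can reach 1% two-sided is 8. At n = 9 the test still reaches 1% if one patient has the smallest-ranked rise (4/512 = 0.0078), whereas at n = 8 it does not (4/256 = 0.0156). The stated 9 is thus consistent with this reasoning, and the present point does not change it.

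**6. Size for the paired comparison.** Illustrative assumption: every other patient falls, with no ties. An affected patient set to no change has a zero difference and drops out of the ranking.

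| Completers | As observed | One set to no change |
|---|---|---|
| 12 | 2/4096 = 0.0005 | 2/2048 = 0.0010 |
| 9 | 2/512 = 0.0039 | 2/256 = 0.0078 |

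Both results stay below 1%, and well below the 0.05 that section 8 uses for the analysis. The consequence lies mainly in the reported improvement rate.

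**The case against.** The strongest objection is that handling of co-treatment belongs in a statistical analysis plan, which may exist and is not shown. That has force for sensitivity analyses. It has less force for the endpoint, because the protocol itself states without condition who is analysed and what counts as improvement. A later plan that scored such a patient as not improved would depart from that wording.

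Second, the withdrawal rule may remove many of these patients. Its examples are not exhaustive, a worsening is recorded as an adverse event, and patients can telephone the investigator. This stands, and the point is confined to those who remain. Recruitment targets acute flares, the site standard for these is an antibiotic, and it is supplied free after the second endoscopy. Nothing in the protocol suggests that these drugs are commonly started within two weeks.

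Third, as-observed scoring is a legitimate choice, and non-response scoring can penalise a patient who had truly improved. That is fair. The statement about direction holds only against the target of improvement without added pouchitis treatment, which is the usual conservative choice when there is no control group.

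A reader might go further in four ways that the documents do not support:

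- **That changes go undetected throughout.** Hospital contact on Days 2-7 makes that unlikely.
- **That the treating gastroenterologist prescribes outside the trial's knowledge.** The text that keeps this physician out of study procedures concerns undue influence at consent, not prescribing.
- **That a new probiotic should also count as failure.** Section 2 lists probiotics as a treatment, but nothing shows that one produces a 3-point fall in this window.
- **That one patient could overturn the result.** Giving that patient the worst rank would yield 2 × 70/4096 = 0.034 with 12 completers and 2 × 33/512 = 0.129 with 9. The protocol calls for no such penalty, and the more natural no-change rule keeps p below 1%.

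**Conclusion.** The point holds as a minor one. For a completer who starts or increases a steroid, immunomodulator or biologic for pouchitis and is not withdrawn, the stated rules score a qualifying fall as improvement due to the study drug.

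How often this happens cannot be derived from the documents, so the figures above are per affected patient and not an expected bias. The paired results also assume that all other patients fall without ties. With 9 completers there is no slack: once the affected patient drops out, 8 remain, and a single rise among them would lose the 1% level (0.0156 at best), though not 5%.

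The documents do not support a claim that the Phase II conclusion is at risk. Section 10 already says that the results cannot settle efficacy.

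**What to change.** Add to section 8:

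- For the 3-point outcome, a patient who starts or increases a steroid, immunomodulator or biologic for pouchitis between Day 1 and the second PDAI counts as not improved.
- In the paired PDAI comparison, that patient is set to no change, or to the observed worsening if that is worse.
- The as-observed result is reported as a sensitivity analysis.
- New probiotic, antidiarrhoeal or antispasmodic use is handled only in sensitivity analyses.

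At the Day 14 concomitant-medication review already scheduled, record drug, indication, start date and dose change. The indication is needed because a steroid may be given for another condition, such as asthma, which the enrollment form lists.

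The cost is a few sentences and one entry on a review that takes place anyway. Patient care, the withdrawal rule and the sample size stay as they are. The downside is that the reported improvement rate may be slightly lower.
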